Heading out of the contradictory results, no publication has reported the in vivo comparison between Papacarie duo and the newly developed CMCR agent Brix 3000 gel in terms of their clinical and radiographic success and their antimicrobial effect compared to the Art approach for caries removal in young immature permanent teeth. The null hypothesis of this study is that no statistically significant difference will be detected between both materials and ART approach regarding to their clinical performance, and their antimicrobial effect in young permanent molars during the follow up period.

AIM OF THE STUDY

Primary aim

- To assess and compare the effectiveness of two chemo-mechanical agents Brix 3000 and Papacarie duo in terms of their clinical and radiographic success in young permanent molars, in comparison with ART approach.

Secondary aims

- Determine the required time for complete caries removal for each method.
- Evaluation of patients' subjective pain reactions following each method.
- Evaluation of antimicrobial effect of two chemo-mechanical caries removal agents by comparing the colony forming units (CFU) at the treatment visit before and after the application of each agent compared to hand excavation method.

MATERIALS AND METHODS

Study design

This will be a randomized, parallel, three-arms controlled clinical trial, with a 1:1:1 allocation ratio. It will be set up and reported according to the CONSORT guidelines.⁽³⁰⁾

The PICOT question is:

Will children (8-10 years old) with class I carious lesion in the first permanent first molar (with ICDAS score 5 or 6) (population; P) using Brix 3000 or Papacarie duo gel (intervention; I) for Chemo-mechanical caries removal in comparison with ART approach (Hand excavation) (Control; C) show a greater success (outcome; O) at different time intervals over twelve months period (time; T)?

Study setting and location

The study will take place in the Department of Pediatric Dentistry and Dental Public Health at the Faculty of Dentistry and the Department of Microbiology and Immunology at the Faculty of Pharmacy, Alexandria University, Alexandria, Egypt.

Sample

Sample size estimation

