The sample size was estimated assuming a 5% alpha error and 80% study power. The overall success rate after 1 year was 95% for chemo-mechanical caries removal,⁽³¹⁾ whereas it was 67% for traditional caries removal.⁽³²⁾ Based on the difference between independent proportions, the sample size was calculated to be 30 patients per group, increasing to 36 patients to make up for lost follow-up cases. Total sample = number per group x number of groups = 36 x 3 = 108 patients.

Software

The sample size was based on Rosner's method⁽³³⁾ calculated by G*Power 3.1.9.7. ⁽³⁴⁾

Eligibility criteria

The participants enrolled in this study will be selected after fulfilling the following criteria:

Inclusion Criteria

- Healthy children aged 8-10 years old.
- The presence of at least one deep carious class 1 lesion in the first permanent molar with a score of 5 or 6 according to the International Detection and Assessment System (ICDAS), detected by visual-tactile inspection to assess lesion severity. ⁽³⁵⁾ (APPENDIX I, Tables 1)

Exclusion criteria

- Children reporting spontaneous or elicited pain from caries or showing any signs of pulpal infection, swelling or abscess.
- Pulpal exposure or bleeding during the excavation procedure
- Children presenting with special health care needs or undergoing medical treatment for chronic or acute diseases affecting salivary flow.
- Allergy or sensitivity to any of the materials included in the study.

Randomization technique and allocation⁽³⁶⁾

- Subjects complying with the inclusion criteria will be randomly assigned to one of the treatment groups, using a computer-generated list of random numbers to either the Brix 3000, Papacarie duo gel group (www.random.org) or ART approach (Hand excavation).
- Allocation will be performed by a trial independent individual and the allocation ratio is intended to be equal (1:1:1).

Allocation concealment⁽³⁷⁾

An assistant will be responsible for giving each participant a serial number that will be used for his/her allocation. A duplicate of this number will be kept in an opaque envelope indicating to which group the patient belongs. This envelope will be kept by a trial independent individual who will be assigned the role of opening it only at the time of intervention; so that the group to which the child is allocated is concealed from the investigator. Grouping Participants will be randomly and equally allocated to one of the three treatment groups:

Grouping

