Participants will be randomly and equally allocated to one of the three treatment groups:

- Test group I (Brix 3000): 36 children meeting the eligibility criteria will be treated using Brix 3000.
- Test group II (Papacarie duo gel): 36 children meeting the eligibility criteria will be treated using Papacarie duo gel.
- Control group: 36 children will be treated using ART approach (Hand excavation).

Blinding⁽³⁸⁾

The investigator will not be blinded to the treatment type. However, the participants, the statistician, and the microbiologist will be blinded to the treatment group.

Materials

- BRIX 3000 gel. *
- Papacarie duo gel. **
- EQUIA Forte HT FIL glass ionomer capsules. ***

Materials for the microbiological assessment

- Mitis Salivarius Bacitracin (MSB) agar (selective culture media for *S. mutans*) prepared according* to the manufacturer's instructions. ****
- Rogosa SL agar plates (selective culture media for lactobacilli), prepared according to the manufacturer's instructions. *****
- Saline as a transport medium.
- Sterile test tubes.
- Sterile plastic Petri dishes.
- Anaerobic gas jar.
- Incubator. *****

* Brix Medical Science. Carcaraña, Santa Fe, Argentina.

** F&A Laboratório Farmacéutico Ltda, São Paulo, Brazil.

*** GC CORPORATION [name].

**** Difco Laboratories Inc, NJ, USA.

***** Himedia Laboratories, Mumbai, India.

***** Red line by binder.

Method

Training and calibration

The main researcher will be trained and calibrated by the study supervisors regarding the use of ICDAS criteria⁽³⁵⁾ in the diagnosis of the teeth to be included in the study, as well as application of both test materials.

Intra-examiner reliability ⁽³⁹⁾

The examination of 10 selected children between 8 to 10 years of age will be carried out followed by re-examination after seven days for the determination of intra-examiner agreement measured by Cohen's Kappa (K). Obtaining a Kappa score ≥ 0.8 is considered excellent reliability. These children will not be included in the study sample.

Baseline examination

- After obtaining the informed consent from the caregiver/parent, (APPENDIX II) the researcher will provide oral hygiene instructions to each of the study participants and will inform them about the importance of maintaining good oral hygiene and a proper diet guidance. ⁽⁴⁰⁾
- All the examinations and interventions will be done by one calibrated examiner.

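### One exclusion criterion, pulp exposure or bleeding during excavation, can be met only after allocation, and no readable text says how the affected children enter the success comparison

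*Combined protocol and SAP*

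**What the plan says.** All references are to the combined protocol and SAP.

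- **Exclusion criteria** list "Pulpal exposure or bleeding during the excavation procedure" beside conditions that can be checked at baseline.
- **Randomization technique and allocation:** "Subjects complying with the inclusion criteria will be randomly assigned to one of the treatment groups". Under **Allocation concealment**, an independent person holds the envelope and is "assigned the role of opening it only at the time of intervention".
- **Intervention:** excavation is the treatment being compared. The gel arms soften the dentin before hand excavation; the control arm uses the hand excavator alone.
- **Blinding** and **Baseline examination:** "The investigator will not be blinded to the treatment type", and "All the examinations and interventions will be done by one calibrated examiner". A periapical radiograph before enrolment checks that the lesion does not already reach the pulp.
- **Grouping:** "36 children meeting the eligibility criteria will be treated using Brix 3000", with parallel wording for Papacarie duo and 36 children for the control arm.
- **Sample size estimation:** 30 per group, "increasing to 36 patients to make up for lost follow-up cases".
- **Clinical evaluation** and **Outcome assessment:** failure is defined by restoration scores 2, 3, 4 or 8, by clinical signs and symptoms, and by radiographic findings. Scores 5 and 6 are removed from the analysis.
- **Statistical analysis:** a chi-square test compares clinical success across the three groups. No analysis population is defined.
- **Study design:** "It will be set up and reported according to the CONSORT guidelines".

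**The concern.** An exclusion criterion is harmless to a randomised comparison when it is settled before allocation. This one cannot be, because the event it names arises during the allocated procedure and may be a consequence of it. If the affected children are removed, the groups compared at 12 months are no longer the groups that were randomised.

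Two features make this more than a formality. The gel step and the visual end point differ between the gel arms and the control arm, so a different event rate by method is plausible, though not shown. The person who decides whether the criterion is met knows the arm, and bleeding is not defined. The comparison at risk is clinical and radiographic success, the primary aim.

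**Working it through.** **1. Timing.** The envelope is opened at the time of intervention, and excavation follows. The radiograph screens for existing pulp involvement only; it cannot detect an exposure that excavation has yet to cause. (The pre-treatment dentin sample is also taken with an excavator and its order relative to the envelope is not stated, but the criterion names the excavation procedure.)

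**2. What happens to these children.** The readable text gives no analysis set, no replacement rule and no reporting by arm for them. The failure definitions do not mention exposure or bleeding during excavation; the nearest rule concerns pulp involvement seen with a radiolucent image. The one explicit removal from analysis, scores 5 and 6, does not mention it either. The increase from 30 to 36 is attributed to lost follow-up. The Grouping text could mean that excluded children are replaced, which would restore the number but not the randomised comparison.

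**3. The plan's own figure.** Inputs: 95% and 67% success, alpha 5%, power 80% (two-sided assumed). Pooled normal formula, mean proportion 0.81:

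n = [1.96·√(2·0.81·0.19) + 0.8416·√(0.95·0.05 + 0.67·0.33)]² / 0.28² = 29.6, so 30 per group, with power 80.5% at 30. The plan's 30 reproduces.

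**4. Possible bias.** The documents give no event rate, so everything here is assumed. Let true success among all randomised be 80% in both arms, e the share of an arm excluded, and q the success probability of an affected tooth. The success rate shown after exclusion is

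(0.80 − e·q) / (1 − e).

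| Event rate, two arms | q = 0 | q = 0.4 | q = 0.8 |
|---|---|---|---|
| 15% vs 5% | 94.1% vs 84.2%, gap 9.9 points | gap 5.0 | gap 0 |
| 10% vs 2% | 88.9% vs 81.6%, gap 7.3 points | gap 3.6 | gap 0 |
| 5% vs 2% | 84.2% vs 81.6%, gap 2.6 points | gap 1.3 | gap 0 |

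Swapping the two rates reverses the sign. Equal rates give no gap.

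**5. In whole children (hypothetical counts).** Start from 34/36 vs 24/36 successes, gel vs control, affected teeth counted among the failures: difference 27.8 points, Fisher p = 0.006.

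- Drop four affected control children: 34/36 vs 24/32, 19.4 points, p = 0.038.
- Drop six: 34/36 vs 24/30, 14.4 points, p = 0.13.
- Drop two gel children instead: 34/34 vs 24/36, 33.3 points, p = 0.0002.

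**6. Loss of numbers matters less.** Excluding 2%, 5% or 10% on top of the implied one-sixth loss leaves 36·(30/36)·(1 − e) = 29.4, 28.5 or 27 per arm, with power 79.7%, 78.4% or 76.1%.

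**7. Price of counting the event as failure.** Take 95% and 67% as success in unaffected teeth, so that success becomes p·(1 − e). Power at 30 per group:

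| Assumed event rate, gel vs control | Success rates | Power |
|---|---|---|
| 2% vs 10% | 93.1% vs 60.3% | 87% |
| 2% vs 2% | 93.1% vs 65.7% | 76% |
| 5% vs 5% | 90.3% vs 63.7% | 70% |
| 5% vs 2% | 90.3% vs 65.7% | 64% |
| 10% vs 10% | 85.5% vs 60.3% | 60% |
| 10% vs 2% | 85.5% vs 65.7% | 43% |
| 15% vs 5% | 80.8% vs 63.7% | 31% |

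**The case against.** The strongest reply is that no sentence says these children leave the analysis. Where the protocol removes cases it says so, as with scores 5 and 6. The trial commits to CONSORT, and the flow chart, a natural place to account for such children, is not shown. This stands in part: removal is the plain reading of an exclusion criterion, but it is inferred. A general commitment to CONSORT does not, however, set aside a specific criterion or supply an analysis set.

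Second, the bias needs three things at once: the children are dropped, the rates differ by arm, and affected teeth fare differently. The radiograph limits how many events occur, and all arms use hand excavators and tactile end points. This stands, and so the concern is conditional. The largest gap above pairs the most extreme assumed rates (about 5 vs 2 of 36 children) with every affected tooth failing. For scale, the standard error of a difference at 80% success with 30 per arm is √(2·0.8·0.2/30), about 10 points.

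Third, counting exposure and undefined bleeding as failure is a choice of outcome. A reader might infer that the radiographic rule on pulp involvement already implies it. It does not clearly do so, because that rule describes a radiographic finding. The possible power loss in step 7 comes from this scoring choice, not from keeping the children in.

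**Conclusion.** The point holds as a gap in the analysis plan: a criterion that can be met only after allocation is applied by an unblinded operator, with no readable rule for the children who meet it. Any bias in the 12-month success comparison could favour either the gels or hand excavation. Illustratively it is 1 to 10 points under the assumed rates, and zero if rates or prognosis are equal.

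A reader might go further and infer that the plan does discard these children, or that one method is favoured by a known amount. The documents support neither: removal is not stated, and no event rate is given. Confidence is therefore moderate. The correction is clearly worth making before results are seen, but this is not a demonstrated flaw in the primary comparison.

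**What to change.** 1. Confine the exclusion criteria to findings made before allocation.
2. Analyse every allocated child in the group to which that child was randomised.
3. Define bleeding for this purpose, and report exposure or bleeding during excavation by arm.
4. State before results are seen how the event enters the success outcome. Counting it as unsuccessful is one option. Show it alongside scoring by the observed follow-up outcome, and an analysis without these children, as sensitivity analyses.
5. Reconcile item 2 with the removal of scores 5 and 6. As it stands, the two would contradict each other, and an affected tooth later re-restored or lost would still drop out through those scores.
6. If the event is to count as failure, say that power at 30 per group may differ from the stated 80%, and give a range such as that in step 7.

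The cost is a few sentences in the eligibility, outcome and statistics sections and one row in the results. No added procedures or enrolment are asked for. The downside is that success rates fall, and power may fall, if the event is scored as failure. Clinical management of an exposed tooth is left to the protocol.

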- No local anesthesia will be administered as it would alter the pain perception of the patient unless necessary.

Evaluations

1. Clinical evaluation

- The clinical assessment will be at 3-, 6- and 12-month intervals to evaluate
 - a) Postoperative pain
 - b) Any signs or symptoms of pulpitis
 - c) Vertical and horizontal percussion tests
 - d) Tooth-color alterations and fistulas presence.
 - e) Restoration success will be evaluated according to the criteria of atraumatic restorative treatment by Phantumvanit et al. (1996) (45). It is based on the retention of the material in the cavity and the presence of secondary caries.
 - f) Restorations which will receive a score of 0, 1 or 7 will be considered successful while those having a score of 2, 3, 4 or 8 will be considered failures. Those which will receive a score of 5, 6 will be excluded from the analysis (Appendix IV).

2. Radiographic evaluation

- Periapical radiograph will be taken immediately after clinical procedure and at 6- and 12-months intervals during follow up period to confirm the clinical evaluation.⁽⁴⁶⁾
- It will be obtained by the long cone paralleling technique to minimize the distortion using the film holders.⁽⁴⁷⁾
- The radiographic evaluation will be performed using the radiographic subtraction method and the assessment of the density of the remaining dentin by gray-scale analysis using the Image j 1.37 V program⁽³¹⁾.
- Therefore, a greater degree of density on the image will indicate a greater success.

- Any case that will exhibit pulp involvement associated with a radiolucent image or any signs for periapical lesions will be considered unsuccessful treatments.

3. Evaluation of time required to perform procedure

- The time needed for complete caries removal will be recorded for each caries removal method.
- The timing of each procedure will set immediately upon the first application by using a stopwatch and turned off when there is no carious dentin left in the cavity.
- After complete removal of decay, the teeth will be restored with glass ionomer filling as a temporary restoration to be replaced after the follow up period using Composite filling sandwich technique.

4. The participants' pain assessment:

- Subjective pain will be assessed after caries removal by means of Wong-Baker faces scale⁽⁴⁸⁾. It consists of faces with different facial expression for happiness and pain and is scored from 0-5 as 0 is very happy and feels no pain and 5 is very painful (APPENDIX III).

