APPENDIX I

Table (1): ICDAS severity criteria⁽⁵⁴⁾

Score	Criteria
0	No change in enamel translucency with prolonged air drying
1	First visual change in enamel (after prolonged air drying)
2	Distinct visual change in enamel
3	Localized enamel breakdown or discolored enamel with no visible dentin involvement
4	Underlying dark shadow from dentin
5	Distinct cavity with visible dentin
6	Extensive distinct cavity with visible dentin

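### ICDAS grade (5 or 6) is scored at entry but used in neither allocation nor analysis; adjusting for it would sharpen the comparisons, chiefly removal time, at no cost

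*Combined protocol and SAP*

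**What the plan says.** Under Eligibility criteria, a child needs at least one deep class I lesion in a first permanent molar scored ICDAS 5 or 6. Appendix I, Table 1 separates the two by extent: score 5 is a distinct cavity, score 6 is "Extensive distinct cavity with visible dentin". Because eligibility depends on the score, the examiner has it before allocation.

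Randomization technique and allocation assigns children "using a computer-generated list of random numbers to either the Brix 3000, Papacarie duo gel group" or to hand excavation, with a 1:1:1 ratio intended. No strata, blocks or minimisation are described. Grouping adds: "Participants will be randomly and equally allocated to one of the three treatment groups", with 36 children in each.

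On outcomes, Evaluations item 3 says: "The time needed for complete caries removal will be recorded for each caries removal method". The stopwatch runs until no carious dentin is left. Restoration success (Evaluations item 1 and Appendix IV) is coded from retention, marginal defects and wear. The Statistical Analysis section plans a chi-square test of clinical success across the three groups and a t-test or Mann-Whitney test for the microbiological samples. It names no test for removal time and no adjustment for lesion grade.

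**The concern.** An extensive cavity plausibly holds more carious dentin to remove and leaves a larger glass ionomer surface open to marginal defect and wear. If so, grade predicts both removal time and the restoration codes that enter clinical success. The trial obtains this predictor at no extra effort and then leaves it out of both design and analysis.

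Two things are at stake. Variation due to grade stays in the error term, which costs precision. And in any one realised allocation, an uneven spread of ICDAS 6 teeth can shift a comparison with nothing in the plan to correct it.

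**Working it through.** **1. The plan's own figure.** Inputs, all from Sample size estimation: alpha 0.05 and power 0.80; 1-year success of 0.95 with the chemo-mechanical method and 0.67 with the traditional one. The resulting size is given as "the sample size was calculated to be 30 patients per group, increasing to 36 patients to make up for lost follow-up cases". Sidedness is not stated; two-sided is assumed. The mean rate is (0.95 + 0.67)/2 = 0.81.

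n = [1.96·√(2·0.81·0.19) + 0.842·√(0.95·0.05 + 0.67·0.33)]² / 0.28² = (1.087 + 0.436)² / 0.0784 ≈ 29.6, so 30 per group. With 6/36 lost, 30/(1 − 1/6) = 36. The stated size reproduces and is not in dispute.

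**2. Size of chance imbalance.** The documents give no ICDAS 5/6 mix, so the ICDAS 6 share q is assumed at 20%, 30% and 50%. The SD of the difference in share between two arms is √(2q(1 − q)/n). The probabilities come from simulating three independent binomial arms.

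| | q = 20% | q = 30% | q = 50% |
|---|---|---|---|
| SD of difference, n = 36 | 9.4 points | 10.8 points | 11.8 points |
| One given pair differs by ≥20 points, n = 36 | 2.7% | 5.3% | 7.6% |
| Some pair differs by ≥20 points, n = 36 | 7% | 13% | 18% |
| Some pair differs by ≥20 points, n = 30 | 17% | 26% | 33% |

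Part of the step from n = 36 to n = 30 is discreteness: 20 points means at least 8 teeth of 36 (22.2 points) but 6 of 30 (exactly 20). Removal time is measured at treatment, so n = 36 applies; 12-month success is closer to n = 30.

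**3. Effect on clinical success.** Take 22 of 36 against 14 of 36 ICDAS 6 teeth, an imbalance of 8/36 = 22.2 points. If success is 10, 20 or 30 points lower in ICDAS 6 (assumed), the difference between arms shifts by 0.222 × 10, 20 or 30 = 2.2, 4.4 or 6.7 points. The planned difference is 95 − 67 = 28 points. Given this imbalance, the simulated two-arm false-positive rate is 6.6% (success 90% in grade 5, 70% in grade 6) or 8.8% (95% and 65%).

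**4. Effect on removal time.** Let ICDAS 6 take k within-grade SD longer (assumed), with half the teeth in each grade. The share of variance due to grade is 0.25k²/(1 + 0.25k²). The information gained by removing it is 1/(1 − share).

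| | k = 0.5 | k = 1 | k = 1.5 |
|---|---|---|---|
| Variance explained by grade | 0.0625/1.0625 = 6% | 0.25/1.25 = 20% | 0.5625/1.5625 = 36% |
| Equivalent gain in patients | 6% | 25% | 56% |
| Shift in mean from the 22-against-14 imbalance | 0.11 SD | 0.22 SD | 0.33 SD |
| Two-arm false-positive rate given that imbalance | 6.6% | 10.4% | 15.2% |

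**5. Averaged over all allocations.** The unadjusted three-arm test stays near nominal: 5.1% to 5.4% for success and 4.8% to 5.1% for time. Stratifying the allocation without adjusting the analysis makes the tests conservative: 4.1% to 4.4% for success and 1.0% to 4.1% for time.

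**The case against.** The strongest reply is that randomisation already deals with this. Chance imbalance is not bias, and step 5 shows the unadjusted tests hold their level over all allocations. That stands. A reader might infer that severity imbalance could drive the success comparison. The documents do not support that: the shift in step 3 is small beside the 28 points the trial is sized for, and removal time is only a secondary aim.

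The prognostic strength of grade is also assumed. No section gives the ICDAS 5/6 mix or any effect of grade on time or success. Entry is limited to deep class I lesions without pulp involvement, which narrows the spread without removing it. This is why weak effects (k = 0.5) are shown beside strong ones.

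A reader might also infer that the list is unrestricted, so that equal arms are out of reach; assigning 108 children independently would give exactly 36/36/36 with probability of only about 0.8%. The documents do not say that. A randomly permuted list of 36 + 36 + 36 fits both the allocation text and the statement in Grouping. The plan does not describe the restriction, but that does not make equal arms unattainable.

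Finally, stratified blocks carry costs of their own. The investigator is unblinded and sees each allocation, so small blocks may become guessable. A child with lesions of both grades has no defined stratum. Both points stand, and they favour adjustment in the analysis over a change to the allocation.

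**Conclusion.** The concern holds as a free improvement. A baseline severity grade that defines eligibility is used in neither the described allocation nor the planned analysis. This does not threaten validity, and it is unlikely to decide the primary result.

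The gain lies mainly in removal time. If ICDAS 6 takes at least 1 SD longer and the grades are evenly split, adjusting is worth about 25% more patients or better. At 0.5 SD it is worth about 6%. For success, adjustment guards against a blurring of a few points. All of these sizes rest on an assumed ICDAS 6 share and assumed effects of grade. What rests on the documents alone is that the grade is known before allocation and that the plan makes no use of it.

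**What to change.** In the Statistical Analysis section:

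- Removal time: name the analysis, for example a linear model on time or log time with arm and ICDAS grade (5 or 6).
- Clinical success: compare the arms with grade as a stratum (Cochran-Mantel-Haenszel) or as a covariate in logistic regression. Failures may be few (30 × 0.05 = 1.5 expected in an arm with 95% success), so state in advance what replaces the logistic model if it cannot be fitted.
- Report ICDAS grade by arm in the baseline table.
- Eligibility requires at least one lesion and all indicated lesions are treated, so say whether the analysis is by tooth, with each tooth's own grade, or by child, with a defined index tooth.

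Stratified permuted blocks by grade are optional. If used, keep grade in the analysis, vary the block sizes and conceal them from the unblinded operator, and define the index tooth that sets the stratum. In either case, one sentence should say how 36 per arm is obtained.

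Cost: a few lines of text, no extra data and no change to the 30 evaluable or 36 enrolled per group. The optional stratification adds a second envelope series.

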- Periapical x-ray radiographs will be taken for each tooth before enrolling it into the trial to determine that the carious lesion depth does not involve the pulp.

Intervention

- All the lesions in the children's oral cavity indicated for treatment will be treated and sampled for microbiological analysis prior to and following caries removal.
- On the day of the intervention, the children will be asked to refrain from tooth brushing in the morning, as well as eating and drinking (except water) for at least two hours before the appointment. ⁽⁴¹⁾

- The patients will be instructed to rinse with a cup of water, then the outer surface of the carious lesion will be washed with a flurry of water to avoid contamination of plaque bacteria. ⁽⁴²⁾
- The tooth will then be partially isolated using cotton rolls and saliva ejector.
- Two portions of dentin will be collected with sterile excavators from the middle of the cavity to perform the microbiological analysis of each tooth before and then after caries removal procedure. ⁽⁴¹⁾
- The dentin sample will then be inserted in a sterile test tube containing 1 mL of saline and transported to the microbiology laboratory within 1-2 hours. ⁽⁴³⁾
- Dentin sample weight will be calculated by measuring the difference between the weight of the whole set (sterilized bottle and transporting medium) and the previously determined weight of the set without dentin. ⁽⁴⁴⁾
- The bacterial count obtained for a given amount of dentin will be used to estimate the number of colonies present in 1 mg dentin (CFU/mg). ⁽⁴⁴⁾
- **In the CMCR group:** either Papacarie duo or Brix 3000 gel will be applied on the carious lesion of tooth and left undisturbed for 30-60 seconds, following manufacturer instructions ⁽²⁸⁾. This produces softening of carious dentin, which will be removed with a hand excavator. This step will be repeated 2-3 times until dentin demonstrates slight resistance with no tug-back sensation when tested with an exploratory probe while pressing an explorer into dentin, then the application of the chemo-mechanical agents will be stopped.
- The visual test for assessment of complete caries excavation will be based on non-turbid appearance of the CMCR agent used.
- **In the ART group** hand excavation will be performed to remove the carious tissue from the cavity by using a sterile sharp hand excavator. The cavity will be determined to be caries-free according to visual and tactile clinical criteria.

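### Participants are declared blinded, but two arms receive a gel and the ART arm does not, so the claim is unsupported for both comparisons with ART

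*Combined protocol and SAP*

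**What the plan says.** The Blinding section has two sentences. One reads "The investigator will not be blinded to the treatment type". The other says that "the participants, the statistician, and the microbiologist will be blinded to the treatment group". The participant claim is not limited to any pair of arms.

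For both chemo-mechanical arms, the Intervention section says the "gel will be applied on the carious lesion of tooth and left undisturbed for 30-60 seconds". The softened dentin is then removed by hand, and "This step will be repeated 2-3 times until dentin demonstrates slight resistance". For the ART arm, "hand excavation will be performed to remove the carious tissue from the cavity by using a sterile sharp hand excavator". On anaesthesia, "No local anesthesia will be administered as it would alter the pain perception of the patient unless necessary".

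Pain is the child's own rating on a 0-5 faces scale after caries removal (Evaluations, item 4). It is a secondary aim and the third item under Study outcome. Under Baseline examination the plan adds that "All the examinations and interventions will be done by one calibrated examiner".

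**The concern.** Blinding of participants is a property of the procedures, and the procedures described here differ in a way that a child in the chair can see and feel. The outcome most exposed is self-rated pain.

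Other child-reported information is exposed too. The quality-of-life questionnaire at one week is self-reported. Postoperative pain is part of the clinical evaluation at 3, 6 and 12 months, and under Outcome assessment a tooth with pain counts as unsuccessful. A symptom that presumably comes from the child therefore also feeds the success outcome.

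If the Blinding section stands, a pain difference between a gel and ART would be published as participant-blinded evidence when expectation could explain part of it. The plan itself leans one way: its list of benefits says the study will support the use of the chemo-mechanical agents. The investigator knows the arm, and no safeguard is written for the pain rating.

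**Working it through.** **The procedures side by side** (Intervention; the anaesthesia rule closes that section)

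| Feature | Brix 3000 and Papacarie duo arms | ART arm |
|---|---|---|
| Gel placed on the lesion | Yes | None described |
| Waiting time per application | 30-60 seconds | None described |
| Applications | 2-3 | Not applicable |
| Hand excavator | Yes | Yes |
| Sham gel, matched wait, eye cover | None described | None described |
| Anaesthesia | Avoided unless necessary | Same |

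Taking 2-3 as the total number of applications, a gel child has between 2 x 30 = 60 and 3 x 60 = 180 seconds of waiting that an ART child does not have. With 36 children per arm, 72 of 108 receive a gel and 36 do not. Of the three pairwise comparisons, the two against ART differ in this way. The two gel arms follow the same written steps.

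**The plan's own figure.** Nothing in the plan quantifies blinding or pain. The only related figure is the arm size, which reproduces. For 95% versus 67% success, two-sided 5% and 80% power, the pooled two-proportion formula is

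n = [1.96 x sqrt(2 x 0.81 x 0.19) + 0.8416 x sqrt(0.95 x 0.05 + 0.67 x 0.33)]^2 / 0.28^2 = (1.087 + 0.436)^2 / 0.0784 = 29.6, or 30 per group.

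Allowing for a loss of one sixth, 30 / (1 - 1/6) = 36. This size was set for clinical success, not pain.

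**Illustration of what a reporting bias could do.** The documents give no SD and no expected effect for pain, so the biases below are assumptions. Suppose there is no true difference, 36 children per arm, a two-sided 5% test, and a bias of d standard deviations between a gel arm and ART. With d' = d / sqrt(2/36) = d / 0.2357, the chance of a significant result is Phi(d' - 1.96) + Phi(-d' - 1.96).

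- d = 0.2: d' = 0.849; 0.133 + 0.002 = 0.136, about 14%.
- d = 0.3: d' = 1.273; 0.246 + 0.001 = 0.247, about 25%.

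On the 0-5 scale with an assumed SD of 1.0 to 1.5, a bias of 0.25 points gives a significant result in the biased direction in about 18% (SD 1.0) to 11% (SD 1.5) of trials. A bias of 0.5 points gives about 56% to 29%. The nominal rate in one direction is 2.5%.

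These are normal approximations for a six-level ordinal score. The Statistical analysis section names no test for pain, so they do not represent the plan's own analysis.

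**The case against.** The strongest reply is that perceiving a gel is not the same as knowing one's group. In a parallel trial each child receives one assigned method, and all three arms use a hand excavator. A child who has never been told of the alternatives, or which is expected to hurt less, may be naive to the comparison. What children and parents are told depends on the consent form, which is not in the review copy.

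This stands in part. A reader might infer that the pain comparison with ART is fully open-label, with each child aware of the arm and the hypothesis. The documents do not show that. But such naivety would not mask the treatment received, and the plan neither claims it nor explains it as the means of blinding.

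A reader might also infer that the unblinded operator collects the pain score. The plan does not say so: the one-examiner sentence sits under Baseline examination and does not mention the child's self-rating. What can be said is that nobody is named for this task.

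The direction of any expectation is not certain either. The Introduction says chemo-mechanical removal is painless in contrast with rotary instruments, but also credits ART with less distress.

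Finally, immediate pain is a secondary outcome, the quality-of-life questionnaire appears in neither the aims nor the study outcomes, and bacterial counts are read by a blinded microbiologist. This limits the reach of the point. It does not rescue an unqualified statement that participants are blinded.

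**Conclusion.** The blinding statement is wrong as written. It is unsupported for Brix 3000 versus ART and for Papacarie duo versus ART, because the described procedures give the child a perceptible gel in one case and none in the other, with no masking step. The main consequence falls on the self-rated pain score, with some reach into the other child-reported measures.

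The conclusion rests on the text alone and needs no assumption about size. The 14% and 25% figures show only what biases of 0.2 and 0.3 SD would do. They should not be read as estimates of this trial's error rate.

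Nor should a reader conclude that the comparison between the two gels is securely blinded. The Introduction gives toluidine blue as the antimicrobial agent in Brix 3000 and chloramine in Papacarie duo, and the plan does not address whether the gels look different. Blinding between the gels is possible but not established.

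**What to change.** 1. Amend the Blinding section to say that children are not blinded to gel versus no gel, and are masked at most as to which gel, provided the two gels cannot be told apart by appearance. If the sponsor relies on children not knowing the other arms, the section should say what children and parents are told.
2. Under the pain assessment, name who presents the faces scale: existing staff other than the operator, preferably unaware of the arm, using a fixed script that does not mention the method.
3. Report gel-versus-ART pain results as not participant-blinded. Call Brix 3000 versus Papacarie duo participant-blinded only if the gels are shown to be indistinguishable to the child.

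The cost is protocol wording, a short script and a little time from a second person at the treatment visit. It needs no additional children and no change to treatment. The downside is a weaker stated claim for the pain comparison with ART.
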